3.1 Overview of Experimental Design

The overarching aim of this project was to compare the traditional recommendation of immediate post-exercise protein consumption with nighttime pre-sleep protein intake during 12 weeks of resistance training on functional and cognitive adaptations in older adults. To achieve this, our design contained three groups who performed the same 12-week RET program two times per week and: 1) Consumed protein immediately post-exercise (Post-ex), 2) Consumed protein 30 minutes prior to sleep (Pre-sleep), or 3) Did not consume additional protein – exercise only (Ex only). Baseline total kilocalories (kcal) and protein intake were monitored to ensure no significant differences among groups occurred. The dependent variables consisted of pre- to post-intervention changes in body composition (i.e. lean mass, fat mass, and percent body fat), functional capacity (i.e. SPPB), nitrogen balance, free plasma insulin-like growth factor 1 (IGF-1), profile of mood states, and sleep evaluation, and digit symbol substitution and pattern comparison. Pre-, mid-, and post-intervention 1-RM, muscular power, and muscle thickness were assessed to determine the time course of muscular adaptations and appetite changes.

The pre-intervention measures took place over 2-3 days. All participants were instructed to refrain from vigorous physical activity at least 48 hours prior to all pre-testing measurements. On day 1, participants reported to the laboratory in the morning following an overnight fast (participants were encouraged to consume normal water intake) to complete the informed consent process, health history, and physical activity questionnaires. Thereafter, participants completed pre-training assessments including height and weight, baseline blood pressure, psychological and cognitive assessments, blood draw (IGF-1), body composition (DXA or BIA),

muscle thickness, muscular power, and the SPPB. Following the completion of day 1 assessments, participants were provided a 3-day food record, actigraphy watch, and 24-hour urine collection jug (nitrogen balance) to return prior to beginning the RET portion of the study.

Day 2 took place approximately 72-96 hours after the first visit and served as a familiarization session for maximum strength testing. Day 3 took place 5-7 days after day 2 and included retesting maximum strength. Some participants elected to complete the first maximum strength test at the end of day 1, in which case, they were instructed to return 5-7 days later to retesting maximum strength, resulting in only 2 pre-testing visits. Thereafter, participants completed 12 weeks of RET, with or without protein supplementation, in the Strength Training Laboratory of the Sandels building. Participants completed post-intervention measures during week 12 in a similar manner as pre-intervention. Maximum strength, muscle power, and muscle thickness were also assessed after week 6 of RET.

3.2 Methods for Specific Aims

3.2.1 Specific Aim 1: Body Composition and Functional Capacity

Specific aim 1 was to examine the degree to which timing of protein intake influenced body composition, muscle thickness, and functional capacity during 12 weeks of RET in older adults.

Dependent Variables (Detailed protocols for each assessment are provided in the subsequent sections)

- Body composition
 - Lean mass
 - Fat mass
 - Percent body fat

- Muscle thickness
- Functional capacity
 - SPPB
 - Balance
 - Gait speed
 - 5-chair stand
 - Maximum muscular strength
 - Muscular power

3.2.2 Specific Aim 2: Cognitive and Psychological Effects

Specific aim 2 was to investigate the extent by which timing of protein intake impacted psychological and cognitive processing speed during 12 weeks of RET in older adults.

Dependent Variables (Detailed protocols for each assessment are provided in the subsequent sections)

- Digit symbol substitution task
- Pattern comparison
- Appetite
- Profile of mood states
- Sleep evaluation

3.2.3 Specific Aim 3: Nitrogen Balance and Free IGF-1

Specific aim 3 was to determine the influence of timing of protein intake on changes in nitrogen balance and free plasma IGF-1 responses during 12 weeks of RET in older adults.

Dependent Variables (Detailed protocols for each assessment are provided in the subsequent sections)

- 24-hour urinary nitrogen balance
- Free plasma insulin-like growth factor 1

3.3 Participants

Healthy, sedentary (not exercising regularly for the past 6 months), older adult males (N=30; Post-ex n=9, Pre-sleep n=11, Ex only n=10) between the ages of 60-75 years old from the Tallahassee area participated in the study. Health-related exclusion criteria included diagnosis of cardiac or peripheral vascular disease, stroke, kidney dysfunction, metabolic diseases, uncontrolled hypertension, orthopedic limitations, skeletal muscle complications, milk allergy, psychiatric conditions, use of psychotropic drugs or cognitive impairment. Additional exclusion criteria included participation in a structured regular exercise program within the past 6 months, actively attempting to increase or decrease body mass, scoring 26 points or less on the Montreal Cognitive Assessment, and/or body mass index (BMI) of ≥ 35 kg/m². To determine exclusion criteria, all participants completed an informed consent (appendix C), health history questionnaire (appendix E), physical activity questionnaire (appendix F), Montreal Cognitive Assessment (appendix G), and height and weight measurements, prior to any participation in the intervention. Lastly, all participants submitted a physician consent (appendix D) form prior to beginning the exercise training protocol.

3.4 Resistance Exercise Training Protocol

All participants completed 12 weeks of RET, 2 times per week on non-consecutive days (separated by 72–96 hours). Participants generally completed their exercise at a consistent time (± 1 hour) throughout the study (e.g., every Monday at 1 pm). Research personnel and certified

personal trainers supervised all RET sessions, which took place in Strength Training Laboratory of the Sandels building. Each resistance exercise session began with 5 minutes of cycling at 50 revolutions per minute at 0.5 kg of resistance on a stationary cycle (Monark 828E, Langley, WA) followed by a standardized dynamic warm-up consisting of body weight movements to prepare the muscles for the specific exercises being performed. Thereafter, participants completed 3 lower body (leg press, leg extension, and leg curl) exercises and 5 upper body (chest press, shoulder press, latissimus row, triceps dip, and biceps curls) and for 3-4 sets and 4-12 repetitions with a 2-3-minute rest period between each set and exercise (see Table 1 for specific details). The chest press and leg press exercises were considered as the primary exercises, while all others were considered as accessory exercises. For the primary exercises, intensity was based upon 1-RM testing results. However, estimated 1-RM values were used for accessory exercises, which were established during week 1 of the RET protocol. Thereafter, a repetitions in reserve-based rating of perceived exertion (RIR-based RPE) scale was used to adjust load accordingly (149, 379). Exercise intensity was adjusted after the mid-testing 1-RM assessment to account for changes in maximum strength. However, for secondary exercises, intensity was adjusted each session based on participants RPE rating.

The 12-week RET program was designed as a periodized mesocycle, comprised of several specific microcycles (Table 1). Week 1 was an introductory microcycle of lower volume and intensity exercise (182). The aim of this week was to acclimate participants to exercise and elicit the repeated bout effect to attenuate muscle damage in the subsequent weeks of the program. On day 1 of the introductory week participants were assigned 2 sets of 12 repetitions at 50% 1-RM and 1 set of 10 repetitions at 55% 1-RM. Thereafter, weeks 2-6 consisted of two subsequent volume-focused microcycles. On day 1 of weeks 2-4, on day 1, participants were

assigned 3 sets of 12 repetitions at 60% 1-RM and 3 sets of 10 repetitions at 65% 1-RM on day 2. On Day 1 of weeks 5-6, on day 1, participants were assigned 3 sets of 10 repetitions at 65% 1-RM and 3 sets of 8 repetitions at 70% 1-RM on day 2. Week 7 consisted of a taper on day 1, which was comprised of 2 sets of 2 repetitions at 80% 1-RM, followed by 1 set of 1 repetition at 85% 1-RM. On day 2 mid-intervention 1-RM assessments were completed for the chest press and leg press exercises followed by the normal exercise protocol for the accessory exercises. Then weeks 8-11 consisted of two subsequent intensity-focused microcycles, where intensity was based upon the mid-testing 1-RM value. For weeks 8-9, participants were assigned 3 sets of 8 repetitions at 70% 1-RM on day 1 and 3 sets of 6 repetitions at 75% 1-RM on day 2. For weeks 10-11, participants were assigned 3 sets of 6 repetitions at 75% 1-RM on day 1 and 4 sets of 4 repetitions at 80% 1-RM on day 2. Week 12 also consisted of a taper on day 1 and post-intervention 1-RM assessment on day 2. Only primary exercises were performed on taper days. Accessory exercises were completed with the same sets and repetitions as the main exercise; however, the load was selected to produce an RPE value between 6-8 and 7-9 for weeks 1-6 and 7-12, respectively. The intensity, sets, repetitions, number of exercises, and rest periods of the exercise program were in agreement with previous literature examining the effectiveness of RET on strength and LBM adaptations in older adults (270, 271).

Table 1. Overview of Exercise Training Program

Week	Focus	Day 1	Day 2
1	Introductory	2x12 @ 50%	2x10 @ 55%
2-3	Volume	3x12 @ 60%	3x10 @ 65%
4	Volume	[contact]%	[contact]%
5-6	Volume	3x10 @ 65%	3x8 @ 70%
7	Taper/Mid 1-RM test	2x2 @ 80%, 1x1 @ 85%	Mid 1-RM test
8-9	Intensity	3x8 @ 70%	3x6 @ 75%
10-11	Intensity	3x6 @ 75%	4x4 @ 80%
12	Taper/Post 1-RM test	2x2 @ 80%, 1x1 @ 85%	Post 1-RM test

RM = Repetition Maximum

If participants were not able complete the prescribed number of repetitions within a set, the training load for the subsequent sets of that specific exercise was reduced by approximately 2.5% for each missed repetition. For example, if a participant was only able to complete 4 of 6 assigned repetitions, then the load for the subsequent sets was reduced by 5%.

3.5 Protein Supplementation

Protein and placebo supplementation were provided in a double-blind, placebo-controlled manner throughout the 12-week intervention. Participants were randomly assigned (<https://www.randomizer.org>) to 1 of 3 groups: 1) Post-ex consumed a protein supplement immediately post-exercise and a non-caloric placebo 30 minutes before sleep, 2) Pre-sleep consumed a non-caloric placebo immediately post-exercise and the protein supplement 30 minutes prior to sleep, or 3) Ex only did not consume protein or placebo supplementation. Participants were instructed to fast for at least 2 hours prior to each exercise session and for 2 hours post exercise (9), except for the consumption of the protein or placebo supplement, along with a 190-kcal snack bar (Nature Valley™, Oats 'N Honey, General Mills, MN), to reduce the timing effects of normal meals on exercise adaptations. Additional instructions were given to consume the nighttime pre-sleep protein or placebo supplement at least 2 hours after their last feeding (e.g. meal or snack) and approximately 30 minutes before sleep with no other food. On non-exercise days, participants were instructed to consume the protein or placebo supplement in between their normal breakfast and lunch.

To ensure a double-blind, placebo-controlled design, an assistant not associated with outcome measures created containers of protein and placebo supplements in advance and did not reveal the identity until the conclusion of the study. Participants were provided two containers with approximately 25 servings (3.5 weeks of supplements) of protein and placebo

supplementations. Each serving was weighed on a digital scale (Etekcity Co., Anaheim, CA) and placed within individual sealable bags (Ziploc; SC Johnson Co., Racine, WI) to ensure accurate servings. Furthermore, both supplements were masked for flavor, and texture. Lastly, participants were instructed to mix their supplement only with water.

The protein supplement (Dymatize Enterprises, Elite XT) consisted of a whey and casein blend (4:1 ratio) containing 40 total g of protein, 15 g of carbohydrates, and 5 g of fat for a total of 265 kcals. This amount has been recommended to maximize muscle protein synthesis in older adults (372) and is the minimum amount to optimally stimulate overnight MPS (340). To assess compliance, participants recorded the date and time of each supplement consumed on a daily compliance sheet. A compliance rate of 80% or greater was required to be included in the analysis.

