3.8 Sample Size Justification and Statistical Analysis

An a priori analysis was conducted with an effect size F of 0.25 calculated using mean and standard deviations from previously reported changes in LBM in older men (350) with power set to 0.8 and α set to 0.05 for 3 groups and 3 measurements. With an expected dropout rate of 15% (110), a sample size of 36 was adequate and provided an even distribution between groups.

A one-way analysis of variance (ANOVA) was used to analyze baseline differences and total training volume among groups. A 3x2 mixed model ANOVA with group as the between subjects' factor (Post-ex, Pre-sleep, Ex only) and time as the within-subjects factor (pre and post) was performed on all dependent variables except for muscle thickness, 1-RM strength, muscle power, and appetite, where a 3x3 mixed model ANOVA (Post-ex, Pre-sleep, Ex only x pre, mid, post) was used. Pearson product-moment correlation, or Spearman's correlation in the event of normality violation, was used to determine the relationship between changes in free IGF-1 and changes in body composition, muscle thickness, 1-RM strength, muscular power, and cognitive assessments.

Outliers were removed and defined as values outside of the mean \pm 3 standard deviations. Data were tested for normality (Shapiro-Wilk), homogeneity of variances (Levene's test), and sphericity (Mauchly's test) where appropriate. When normality or homogeneity of variances was violated, non-parametric testing or data transformation was performed. For a mixed model ANOVA, if transformation could not correct the violation, original data were analyzed, as there are no non-parametric alternatives. When sphericity was violated, the main time and group x time interactions were interpreted with the Greenhouse-Geisser estimation.

Significance was set at $p \leq 0.05$. Trends were noted for p -values between 0.051-0.10. For significant interactions and main effects, pairwise comparisons with Bonferroni adjustments were conducted (296, 332). Pearson correlation coefficients (r) or Spearman's correlation coefficients (r_s) were interpreted as "negligible" = < 0.30 , "low" = $0.30-0.50$, "moderate" = $0.50-0.70$, "high" = $0.70-0.90$, and "very high" = > 0.90 (244). Percentage change was calculated as $((\text{post value} - \text{pre value}) * 100)$. All analyses were performed with SPSS version 25

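### The 80% supplement-compliance rule can remove men from Post-ex and Pre-sleep but never from Ex only, so contrasts with Ex only are open to selection bias of unknown size and direction

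*Combined protocol and SAP*

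**What the plan says.** All references are to the combined protocol and SAP.

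- **Inclusion rule (3.5).** "A compliance rate of 80% or greater was required to be included in the analysis". The preceding sentence says how compliance is measured: "participants recorded the date and time of each supplement consumed on a daily compliance sheet".
- **Arms (3.5).** Allocation is random. One arm is described as "Post-ex consumed a protein supplement immediately post-exercise and a non-caloric placebo 30 minutes before sleep", the second as "Pre-sleep consumed a non-caloric placebo immediately post-exercise and the protein supplement 30 minutes prior to sleep". For the third, "Ex only did not consume protein or placebo supplementation".
- **Analysis (3.8).** Every outcome goes into a mixed ANOVA with the three groups as the between-subject factor. Bonferroni-adjusted pairwise comparisons follow significant effects. There is no all-randomised analysis, no sensitivity analysis, and no adherence rule that could apply to Ex only, such as session attendance.
- **Numbers.** Section 3.8 says that "a sample size of 36 was adequate and provided an even distribution between groups". Section 3.3 reports "N=30; Post-ex n=9, Pre-sleep n=11, Ex only n=10". Neither section says whether those 30 men are counted before or after the compliance rule, and no exclusions are reported by arm.

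**The concern.** Randomisation makes the arms comparable only for the men as allocated. Here entry to the sole planned analysis depends on behaviour after allocation, and that behaviour can be observed in only two of the three arms. A man in Post-ex or Pre-sleep who takes too few servings drops out of the analysis. A man of the same disposition in Ex only stays in.

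If men who keep to a supplement schedule also differ in how they respond to training, eat or sleep, the filtered arms no longer match Ex only. That affects two of the three pairwise contrasts and every three-group test. Those two contrasts are also the only ones that compare added protein with none.

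The threshold itself is ambiguous as well: section 3.5 does not say whether 80% applies to each supplement or to both pooled.

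**Working it through.** **1. Where the rule can act.** Set side by side, the statements in 3.5 settle this. Compliance is measured on supplements; Post-ex and Pre-sleep each take two products; Ex only takes none. The rule has nothing to act on in Ex only. Between Post-ex and Pre-sleep the threshold, the number of products and the schedule are the same, so that contrast lacks the one-sided filter, although it still compares compliers only.

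**2. How many men could have been removed.** The documents do not say. A bound needs three assumptions: 36 men were randomised, 12 per arm (36/3); the 9/11/10 in 3.3 is the count after the filter; and every missing man in a supplemented arm was a compliance exclusion.

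| Arm | Assumed randomised | Reported | Shortfall |
|---|---|---|---|
| Post-ex | 12 | 9 | 3/12 = 25% |
| Pre-sleep | 12 | 11 | 1/12 = 8.3% |
| Ex only | 12 | 10 | 2/12 = 16.7% (cannot be due to this rule) |

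The two supplemented arms together are short by 4/24 = 16.7%, the same as Ex only, so the counts show no excess loss. If 9/11/10 is a count before the filter, this bound does not apply.

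**3. Size of the shift.** Treat compliance as normal, remove the lowest share p, and let r be the correlation between compliance and change in outcome (assumed; the documents give none). In units of the within-arm SD of change:

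shift = r × φ(z_p) / (1 − p), where z_p is the p-quantile of the standard normal and φ its density.

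| p excluded | φ(z_p)/(1 − p) | r | Shift (SD) |
|---|---|---|---|
| 5% | 0.109 | 0.1 | 0.011 |
| 1/12 | 0.167 | 0.3 | 0.050 |
| 15% | 0.274 | 0.3 | 0.082 |
| 25% | 0.424 | 0.3 | 0.127 |
| 25% | 0.424 | 0.5 | 0.212 |

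The sign follows the sign of r, so the direction is open. A shift of 0.25 SD with 25% excluded would need r = 0.25/0.424 ≈ 0.59.

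**4. Against the noise.** The standard error of a two-arm difference is √(1/10 + 1/10) = 0.447 SD for 10 per arm. With the reported counts it is √(1/9 + 1/10) = 0.460 for Post-ex versus Ex only and √(1/11 + 1/10) = 0.437 for Pre-sleep versus Ex only.

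For a nominal two-sided 5% test with no true difference (normal approximation, 10 per arm), the rejection rate is P(Z > 1.96 − d) + P(Z < −1.96 − d), with d = shift/0.447:

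- shift 0.08 SD, d = 0.18: 5.4%
- shift 0.15 SD, d = 0.34: 6.3%
- shift 0.21 SD, d = 0.47: 7.6%

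These rates are for a single unadjusted contrast. Simulating the planned sequence on change scores (three-group test, then Bonferroni) with 9/11/10 and shifts of 0.21 and 0.08 SD in the two supplemented arms moves the three-group rate from 5% to about 6.5%. A declared difference between Post-ex and Ex only goes from about 1.6% to 2.7%.

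**5. What the undefined denominator changes.** Assume one serving of each supplement daily for 12 × 7 = 84 days.

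- Pooled: 168 servings, 80% = 134.4, so a man fails at 34 missed servings.
- Per supplement: 84 servings, 80% = 67.2, so a man fails at 17 missed servings of either product.

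Under the pooled reading a man could miss 33 of 84 protein servings (39%) and still count as compliant.

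**The case against.** The strongest reply is that the study is mainly about timing. The overarching aim in 3.1 and all three specific aims in 3.2 concern when protein is taken, and for Post-ex versus Pre-sleep the rule is symmetric, with masked products. The threshold is fixed and does not depend on outcome. Restricting to compliers is also a recognised choice for an efficacy question. This stands, and it limits the reach of the point. It does not remove it, because Ex only is a designed arm in every ANOVA, and a compliers-only set is here the sole analysis and is not labelled as such.

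A second reply is that no exclusion is shown and the arm shortfalls are balanced. That is true, and the bias may be zero. But equal counts do not show equal reasons: losses in Ex only cannot come from this rule, while losses in the other arms may. Supervised training (3.4) may also weaken any link between compliance and training effort.

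A third reply is that the 5.4% to 7.6% rates are not those of the planned test. That is correct. Under the planned sequence the absolute rates are lower, and the larger figures should be read only as the effect on one unadjusted contrast.

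Finally, exclusion counts are results, and a methods text need not carry them. That is fair for the counts, but not for the rule, which is stated in the plan.

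**Conclusion.** The concern holds. As written, the rule can filter Post-ex and Pre-sleep and can never filter Ex only, and no planned analysis avoids it. That follows from the text and needs no assumption.

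The consequence is less certain. Bias is possible but not demonstrated. It is zero if nobody was excluded or if compliance is unrelated to outcome, and the documents do not let a reader tell which case applies. On the assumed ranges (5% to 25% excluded, r from 0.1 to 0.5) the shift in a filtered arm is 0.01 to 0.21 SD, less than half the standard error of a two-arm difference. That is modest, but it does not show in any p-value or interval. It should be fixed, mainly because the remedy is cheap.

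**What to change.** - Make the main analysis all randomised men with available outcome data, in the arm assigned, whatever their supplement compliance.
- Keep the 80% compliers as a labelled sensitivity analysis, limited to Post-ex versus Pre-sleep, where the rule exists in both arms.
- Report per arm the number randomised, the number excluded for compliance and the number lost for other reasons, and say which of these counts the 9/11/10 in 3.3 represents.
- State whether 80% applies to each supplement or to both pooled.

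The cost is one re-analysis and a few lines of reporting. The re-analysis is possible only where the excluded men's outcomes were measured. The downside is some dilution of the main estimate by non-compliance. If no man was excluded under the rule, one sentence saying so closes the question of bias.

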3.6 Food Records and Analysis

Participants were instructed to maintain their normal dietary habits throughout the intervention, except for the consumption of either protein or placebo supplement. At pre- and post-intervention assessments, participants were asked to complete a written 3-day food record consisting of two weekdays and one weekend day of habitual dietary patterns, which was collected and used for dietary analysis. Participants were encouraged to provide photos of meals and diet logs were reviewed with research personnel after submission to enhance accuracy of the recorded food intake. Additionally, throughout the study participants were queried about changes to their dietary habits. Lastly, dietary analysis was performed by the same person for all diet logs using the MyFitnessPal® website (10).

